3.1 Inclusion Criteria

- 1) Patients either male or female over the age of 18 (who can consent for themselves) in good general health.
- 2) The selected teeth needed to be in occlusal function with a natural tooth and in interproximal contact with two adjacent natural teeth.

- 3) Molar or premolar teeth with suspected endodontic problems that require root canal treatment.
- 4) Teeth should not be mobile and must be restorable.

3.2 Exclusion Criteria

- 1) Pregnant women, in view of requirements for radiographs (or if they could possibly be pregnant). To be confirmed by the Medical History Questionnaire.
- 2) Patients younger than 18.
- 3) Patients unable to give consent.
- 4) Teeth with probing periodontal depths greater than 5 mm.
- 5) Non-restorable teeth.
- 6) Not involving patients from prisons.
- 7) Not involving patients who cannot read, write or understand English

3.3 Withdrawal of Subjects

The participant would be withdrawn from the study if he or she no longer wishes to participate in the study or has relocated and will be unable to attend. Data or tissue, which is not identifiable to the research team, may be retained. Any identifiable data or tissue would be anonymised or disposed of.

4. Assessment of Efficacy

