2.1. Trial Objectives

Aims and Objectives:

The clinical trial aims to investigate whether varying amounts of residual tooth structure have an influence on the success and survival rate of endodontically treated teeth and/or restoration at 1-2 years post treatment by using Cone Beam Computed Tomography (CBCT).

Primary and Secondary endpoints:

The principal outcome of the study is to assess the success and survival of endodontically treated teeth and restoration at 1 and -2 years post treatment restored using CAD CAM restorations. The secondary outcome measure is to assess the survival of the CAD CAM restorations on root canal treated teeth and determine the main types of failure.

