2.2 Trial Design & Flowchart

The study is a case control comparing the success and survival rate of endodontically treated teeth with varying degrees of tooth structure loss restored using CAD CAM restorations.

[figure not shown]
Patients requiring endodontic treatment will be assessed clinically and radiographically and divided into groups defined according to the residual coronal dentin after root canal treatment into four groups (less than 33% , 33%-50%, 50%-66% and more than 66% of tooth structure remaining). The endodontic treatment and final restoration will be accomplished by Endodontic McInDent Postgraduates Students (Endodontic Postgraduate Unit, Guy's Hospital, Guy's & St. Thomas' NHS trust) who will be trained

to ensure standardisation of the endodontic and operative procedures by using one of the indirect/direct restorations.

Dental periapical radiograph and Cone Beam Computed Tomography (CBCT) scans will be taken at baseline, 12 months and 24 months. The patients will be sent a reminder to attend the follow up by email, letter or SMS. Clinical assessment and radiographical evaluation of Cone Beam Computed Tomography (CBCT) scans will be carried out immediately after endodontic treatments have been accomplished and 1 and 2 years post operatively and will be assessed independently by a group of examiners.

Four examiners (Endodontists n=2, Radiologists n=2) will view the randomised images under standardised conditions. The examiners will also be trained on how to interpret CBCT data before looking at images. The restorations will be assessed clinically.

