2.3 Trial Flowchart:-

2.4 Trial Statistics

2.4.1 Sample Size

The sample size calculation for this study was based on chi-test for testing the association between tooth surface lost (<33%, 33-66% and >66%) and Root Canal Treatment status (Success or Failure). A study with an effect size of 0.3 and a power of 80% will require a total sample of 108 to test the association at 5% levels using two tailed test. The power calculation was carried out using Gpower 3.1.7.

In a previous study by Ferrari et al. (2012), a sample of 345 patients provided 6 groups of 60 premolars each in need of endodontic treatment. Groups were classified according to the number of remaining coronal walls before abutment build-up. Within each group, teeth were allocated to one of three subgroups: (A) no post retention; (B) prefabricated post; or (C) customized posts (N = 20). The authors found that failure risk was lower in teeth restored with prefabricated ($p = 0.001$) than with customized posts ($p = 0.009$). Teeth with one ($p = 0.004$), two ($p < 0.001$), and three coronal walls ($p < 0.001$) had significantly lower failure risks than those without ferrule and similar failure risks existed for teeth without coronal walls, regardless of the presence/absence of ferrule ($p = 0.151$). Sample size calculation for this study was based on comparing success rates for the four groups using chi-square test. This study designed to have 80% power to detect the difference in success rates between the four groups at 5% level of significance with an effect size of 0.35 using a two-tailed test. Assuming a dropout rate of 25% at the end (after 2 years of root canal re-treatment), it requires a sample size of 120

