4.1 Efficacy Parameters

Parameters used to assess efficacy of the study will depend upon the participant's signs and symptoms, clinical examination and radiographical assessment.

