4.1.2 Secondary Efficacy Parameters

The survival of teeth and or restoration in the oral cavity.

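### Section 3.3 withdraws patients who have moved and cannot attend from the whole study, so tooth-survival data that a willing patient could give without a visit are lost

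*Protocol*

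**What the plan says.** Protocol 3.3 states: "The participant would be withdrawn from the study if he or she no longer wishes to participate in the study or has relocated and will" (the sentence ends by requiring inability to attend). The second limb has two conditions, since the patient "has relocated and will be unable to attend". Both limbs lead to withdrawal from the study. The section continues: "Data or tissue, which is not identifiable to the research team, may be retained"; identifiable data are to be anonymised or disposed of.

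Survival appears twice as an outcome. Section 2.1 says "The principal outcome of the study is to assess the success and survival of endodontically treated teeth and restoration", and 4.1.2 gives as the secondary efficacy parameter "The survival of teeth and or restoration in the oral cavity". Section 4.1 says that the efficacy parameters "will depend upon the participant's signs and symptoms, clinical examination and radiographical assessment", and 2.2 has restorations assessed clinically. Recall visits are at 12 and 24 months (4.2).

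The only remote contact described is in 2.2: "The patients will be sent a reminder to attend the follow up by email, letter or SMS". Section 2.4.1 plans for loss: "Assuming a dropout rate of 25% at the end (after 2 years of root canal re-treatment), it requires a sample size of 120". Section 2.4.4 names Kaplan-Meier and Cox regression, worded around the success rate, and gives no rule for censoring or missing data. The SAP is a power statement and does not address follow-up.

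**The concern.** Withdrawing consent and ceasing to attend are different events. The first ends the right to collect data. The second ends only the data that need a visit: the CBCT reading, the percussion and mobility findings, and the examination of the restoration. Whether the tooth is still in the mouth, and when it was extracted if it is not, is something an adult can report in a short message. Section 3.3 does not make this distinction, so a willing patient who has moved away stops contributing to tooth survival along with success.

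Two things are at stake. First, avoidable missing data on an outcome named in both 2.1 and 4.1.2. Second, bias, if the patients who are lost fail more or less often than those who stay. The comparison is between non-randomised bands of remaining tooth structure, and the study asks whether outcome differs between them. Loss related to failure could therefore distort the comparison of bands as well as the overall rate. Making identifiable data anonymous on withdrawal could also remove the link needed to add a later tooth outcome to the patient's record.

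**Working it through.** **1. The plan's own figure.** Inputs from Protocol 2.4.1: four groups (df = 3), effect size w = 0.35, 5% level, 80% power, 25% dropout. Power is the probability that a noncentral chi-square variable with 3 df and noncentrality N·w² exceeds the 5% critical value. The smallest N reaching 80% is 90 (noncentrality 90 × 0.35² = 11.025; power 80.5%). Inflating for dropout gives 90 / 0.75 = 120, which matches the plan. Up to 30 losses (120 − 90) are already allowed for.

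**2. How many patients the rule could affect.** The documents do not say what share of the dropout is relocation. Call it s (an assumption). The number affected is 30·s. If all of them answered a message, survival status would be known for 90 + 30·s.

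| s | Affected, 30·s | Survival status known | Power at that N (w = 0.35, df = 3) |
|---|---|---|---|
| 0 | 0 | 90 | 80.5% |
| 0.25 | 7.5 | 97.5 | 83.8% |
| 0.5 | 15 | 105 | 86.7% |
| 0.75 | 22.5 | 112.5 | 89.1% |
| 1 | 30 | 120 | 91.1% |

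The last column borrows the effect size set for success, because the plan sets none for tooth survival. It shows scale only. The row s = 1 cannot be reached if any of the 30 withdraw consent, and incomplete response would lower every row but the first. For the visit-based success outcome, N stays at 90 throughout.

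**3. Illustration of bias.** Assumptions, none of them from the documents: 10% true tooth loss at 2 years (12 of 120), and lost patients failing at k times the rate of the others. Let d be the fraction of all patients who are lost, with every event among them unseen. Then:

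- failure rate among those observed = 0.10 / [(1 − d) + d·k]
- share of events unseen = d·k / [(1 − d) + d·k]

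| | k = 1 | k = 2 | k = 3 |
|---|---|---|---|
| d = 0.25 (all 30): observed rate | 10.0% | 0.10/1.25 = 8.0% | 0.10/1.50 = 6.7% |
| d = 0.25: events unseen | 25% | 0.50/1.25 = 40% | 0.75/1.50 = 50% |
| d = 0.125 (15, s = 0.5): observed rate | 10.0% | 0.10/1.125 = 8.9% | 0.10/1.25 = 8.0% |
| d = 0.125: events unseen | 12.5% | 0.25/1.125 = 22% | 0.375/1.25 = 30% |

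At d = 0 there is no effect. At k = 1 data are lost but the rate is not biased. The rows for d = 0.25 are the upper end for the number lost. All entries are crude proportions, not Kaplan-Meier estimates, and they ignore events already seen at 12 months, so they overstate the unseen share for patients lost only in the second year.

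**4. What can be reported without a visit.** Tooth presence and the date of an extraction can. Restoration status is weaker: 2.2 has restorations assessed clinically, and 4.2 identifies debonding, fracture and core failure by clinical examination. A patient can report that a restoration was lost or replaced, but not reliably a partial fracture. The means exist: 2.2 already provides email, letter and SMS, and 3.2 excludes patients who cannot read, write or understand English.

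**The case against.** The case on the other side has several parts, and much of it stands.

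- A reader might infer that everyone who moves is withdrawn. The text does not say so: the patient must also be unable to attend.
- A reader might infer that 3.3 is what loses the patient whose tooth was extracted elsewhere and who never comes back. That patient is a non-attender, and 3.3 does not withdraw non-attenders. Moving house is less plausibly related to tooth failure, so the rule by itself may cause missing data with little bias. What remains is that for such patients, too, the only contact described is a reminder to attend.
- A reader might infer that the planned Kaplan-Meier estimate of tooth survival is overstated by a known amount. Section 2.4.4 ties those methods to the success rate, no separate analysis of tooth survival is named, and no censoring rule is given. The direction and size of any bias cannot be read from the documents.
- A reader might count all 30 expected dropouts as recoverable. Some will have withdrawn consent and may not be approached, and the relocation share is not stated.
- That survival can be learned without a visit is an inference, and 4.1 points to examination and radiographs. The inference is sound for tooth presence and weak for restorations.
- Data collected before withdrawal may be kept if not identifiable, and the dropout allowance protects the stated power. Both are true, but neither supplies what happened to the tooth afterwards.
- The consent pages and flowcharts are not available, so permission for later contact may already exist.

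**Conclusion.** The point holds in limited form. Section 3.3 ends follow-up for willing patients who have moved and cannot attend, exactly as for withdrawn consent, and no available text plans to learn the fate of the tooth by any other route. This discards obtainable data on tooth survival. Any loss related to failure would bias the survival estimates, but whether it is related is unknown.

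The number affected lies between 0 and 30, less those who withdraw consent. The bias figures (10% read as 8.0% or 6.7% if all 30 are lost and fail at two or three times the rate of the others) rest wholly on assumed inputs and are illustrative only. There is no error in the sample-size arithmetic on this point, and the visit-based success outcome is not affected by the proposed change. Label: cheap improvement.

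**What to change.** In 3.3, separate (a) withdrawal of consent from (b) stopped attendance, including relocation. Keep patients in (b) in the study, with their data still linkable. At 12 and 24 months, ask them by email, letter or SMS whether the tooth is still present, the date of any extraction, and whether the restoration has been lost or replaced.

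Use tooth presence and extraction date for tooth survival. Treat patient-reported restoration status as supportive only. Keep success visit-based. Add permission for this contact to the consent form if it is not already there.

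The cost is protocol wording, possibly consent wording, and a short message at two time points to at most 30 patients on the plan's own dropout figure, through channels already in use. The downside is that survival would then mix examined and patient-reported sources, so flag the reported data and show survival with and without them.

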4.1 Efficacy Parameters

Parameters used to assess efficacy of the study will depend upon the participant's signs and symptoms, clinical examination and radiographical assessment.

4.1.1 Primary Efficacy Parameters

The primary efficacy parameter will be the success of teeth in relation to the absence of any signs and symptoms, endodontic or restorative failures.

4.1.2 Secondary Efficacy Parameters

The survival of teeth and or restoration in the oral cavity.

4.2 Procedures for Assessing Efficacy Parameters

Patients will be recalled after 12 and 24 months for clinical and radiographical assessments. Four examiners other than the operator independently performed evaluation of success or failure.

Clinical examination should reveal the absence of the following events which considered if present as 'relative' failures: restoration debonding, restoration fracture, failure of the core portion requiring a new coronal restoration, and no mobility of the teeth or tenderness to percussion. While root fractures leading to tooth extraction were considered as 'absolute' failures.

CBCT scans assessment should reveal the absence or reduction of any radiolucencies or widening of the apical periodontal ligament space and vertical or horizontal root fracture.

5. Assessment of Safety

5.1 Specification, Timing and Recording of Safety Parameters

Measures that will be taken to ensure the subject's safety during the study are the same as with any routine dental procedure.

5.2 Adverse Event (AE)- Any untoward medical occurrence in a subject to whom a medicinal product has been administered, including occurrences which are not necessarily caused by or related to that product

- Syncope/ transient loss of consciousness during dental procedure or medical emergencies of a mild nature that are managed at chair side.

5.3 Adverse Drug Reaction (ADR) - Any untoward and unintended response in a subject to an investigational medicinal product which is related to any dose administered to that subject.

- Sodium hypochlorite used in root canal treatment is known to cause an adverse reaction of pain/ swelling if accidentally extruded beyond the root apex. These are rare and not expected to be reported

5.4 Serious Adverse Event or Reaction (SAE/SAR) - A serious adverse event is defined as an adverse experience that results in any of the following outcomes:-

- death
- a life-threatening adverse experience (any adverse experience that places the patient or subject, in the view of the investigator, at immediate risk of death from the reaction as it occurred, i.e., it does not include a reaction that, had it occurred in a more severe form, might have caused death)
- inpatient hospitalisation or prolongation of existing hospitalization
- a persistent or significant disability/incapacity (a substantial disruption of a

- person's ability to conduct normal life functions)'
- a congenital anomaly/birth defect.

Where GSTT is the Sponsor and the SAE is related (that is, it resulted from administration of any of the research procedures), to the study procedures or is an unexpected occurrence (that is, the type of event is not listed in the protocol as an expected occurrence) then it must be reported immediately upon knowledge of the event to R&D and always within 24 hours. For all other AEs these must be reported to GSTT when copied into the Annual Progress Report.

The definition of "serious" may be defined differently within the protocol and it is the responsibility of the research team to adhere to the protocol definition in terms of SAE reporting. Additionally the protocol and other documentation may identify SAEs that do not need immediate reporting and SAEs falling under these categories should be recorded and reported according to the protocol. Where GSTT is the Sponsor and an SAE occurs that does not require immediate reporting, this SAE should be reported in the Annual Progress Report and copied to R&D. All adverse events that are to be reported to R&D Directorate must be signed and dated and completed by the Investigator.

6. Definition of the End of Trial

The end of trial is after the end of visit five (twenty forth month follow-up). Following that, patients will be reviewed normally either at their GDP or at Guy's Hospital.

7. Direct Access to Source Data and Documents

The investigators and KCL will permit trial-related monitoring, audits, REC review, and regulatory inspections (where appropriate) by providing direct access to source data and other documents such as patients' case sheets and notes.

8. Ethics & Regulatory Approvals

The study will be conducted in compliance with the principles of the Declaration of Helsinki and the principles of GCP. Any subsequent protocol amendments will be submitted to the REC, and the REC will be provided with progress reports, and a copy of the Final Study Report.

9. Quality Assurance, Data Handling, Publication Policy and Finance

Patients will be allocated a unique identification number. The Principal Investigator will maintain a database of the patient's personal data, clinical notes and treatment records. This will be stored in the office of the Chief Investigator [name] in [name], Guy's Hospital. Only the chief investigator and researchers will have access to the participants' personal data during the study. The personal data will be stored for 6 months and the research data for 3 years after the study has ended. The trial will be registered on the GSTFT NHS R&D database and a public database: clinicaltrials.gov. The results of the study will be published in peer reviewed scientific journals, internal reports and in conference presentations. The study is self-funded.

10. References

1. Schilder, H., *Filling root canals in three dimensions*. Dent Clin North Am, 1967: p. 723-44.

Title of Project: "Success and survival of root canal treated tooth restored using ceramic onlays"

Name of Researcher: [name], [name], [name]

Name of Statistician: [name]

Please find below the power calculation statement.

Power Calculation Statement:

The sample size calculation for this study was based on chi-test for testing the association between tooth surface lost (<33%, 33-66% and >66%) and Root Canal Treatment status (Success or Failure). A study with an effect size of 0.3 and a power of 80% will require a total sample of 108 to test the association at 5% levels using two tailed test. The power calculation was carried out using Gpower 3.1.7.

Regards,
[name].
[contact]
12/04/2017
